14.1.5 Specification of the Covariance Model

The model for the mean uses the actual times of the visits as a continuous variable instead of the scheduled visit times. Therefore, the covariance model will also use the actual visit times, using random effects. For valid inference, the model for the covariance should be correctly specified.

Thus, the preference will be for models with relatively many parameters in order to ensure robust estimation of the covariance, though this may lead to a loss of efficiency.

Therefore a model will be specified with four per patient random effects: intercept, t , t^2 , t^3 , with an unstructured covariance matrix. This covariance model contains 11 parameters, ensuring sufficient robustness. In case the model does not converge, or the covariance matrix is not positive definite, we will drop terms from the highest order random effect.

14.2 Supplementary Analyses for the Primary Endpoint

Supplementary analyses can provide additional insights into the understanding of a treatment effect.

14.2.1 ANCOVA

The population-level summary for the variable will be altered. An analysis of covariance (ANCOVA) model will be performed on the changes from baseline in FEV_1 to Week 48, using the same stratification factors and the same covariates described for the LMM for the primary efficacy analysis (except for time factors). In case of death or re-transplantation events, FEV_1 will be imputed as zero at each nominal day post event.

In case of violation of the normality assumption even after log transformation (section 14), then rank transformation will be applied to normalize the data. The same ANCOVA model will be applied to the rank-transformed data.

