14 EFFICACY

For each efficacy analysis, the adequacy of the model assumptions will be checked, and if it is found that these are inadequate then alternative approaches may be performed.

For all variables assumed to be normally distributed, the conditional studentized residuals from this model will be tested using the Shapiro-Wilk test. If the assumption of normality of these residuals is violated, then a log-transformed model will be fitted. The need for a possible log transformation of these variables will be investigated prior to unblinding by assessing the model

residuals without a treatment term. Where data are transformed for analysis, back transformation will be applied for the presentation of results. Presentation of the tables will be amended as needed for this, with the addition of an explanatory footnote.

Classification and imputation of missing data will be completed prior to any transformation of the data for analysis.

As a general remark for all efficacy endpoints based on spirometry data, values collected at 1h and 4h post dose will not be used for any efficacy analyses as they are collected only for safety evaluations.

It is important to note that due to the decrease in sample size (see section 8.2) the study will be underpowered for the assumed effect to assess the statistical hypothesis for the primary endpoint. The statistical modelling for the primary endpoint for the pre-specified covariates may lead to non-convergence of the models and selective covariates will have to be considered. Supplementary analyses for the primary endpoint, **CCI** will adopt simple statistical analyses. As a result, all analysis for this study will be descriptive in nature.

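### If normality fails, the supplementary ANCOVA moves to ranks of an unnamed type, loses its estimate in litres, and cannot satisfy the SAP's own back-transformation rule

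*SAP*

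**What the plan says.** SAP section 14 sets a general rule for efficacy variables assumed normal: "the conditional studentized residuals from this model will be tested using the Shapiro-Wilk test". If normality is violated, a log-transformed model follows. The need for the log is judged before unblinding, from a model without a treatment term. The same section adds: "Where data are transformed for analysis, back transformation will be applied for the presentation of results".

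Section 14.2.1 adds a further step for the ANCOVA only. If normality is still violated after the log, "rank transformation will be applied to normalize the data", and "The same ANCOVA model will be applied to the rank-transformed data". It says that the population-level summary is altered but does not name the new one. Nor does it say whether the untransformed result stays in the table, or whether normality is tested again after ranking.

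On failures, section 14.2.1 states: "In case of death or re-transplantation events, FEV_1 will be imputed as zero at each nominal day post event". Such a patient's change is therefore minus his or her own baseline. The primary endpoint is in litres (section 7.3), and section 14 declares that "all analysis for this study will be descriptive in nature".

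**The concern.** In a descriptive study the useful output is an estimate with an interval on a scale that clinicians can read. Here that scale is litres, because the trial was designed around 0.2 L. On its natural reading, section 14.2.1 lets a normality test replace the litre-scale ANCOVA with a model whose treatment coefficient has no unit.

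Three details make this worse than a matter of taste. The stated purpose, normalizing, is not what simple ranking does. The back-transformation rule in section 14 and the rank step in section 14.2.1 cannot both be followed. And the zero imputation, which entered in the same SAP version (3.0) as the ranked ANCOVA, makes the trigger likely.

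At stake is the only covariate-adjusted Week 48 estimate in the visible text that does not depend on the spline and random-effects model. Section 14 itself warns that the primary model may not converge, so this cross-check has value.

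**Working it through.** **Inputs from the documents.** 62 patients randomized 1:1; design difference 0.2 L; SD of change 0.35 L (SAP sections 7.2 and 8.2); drop-out about 10% (protocol synopsis), so roughly 62 × 0.9 ≈ 56 patients with Week 48 data. The plan gives no figure for the rank fallback. Its sample size does reproduce: with 0.2 L, SD 0.35 L and one-sided 0.025, t-test power is 0.7996 at 49 and 0.808 at 50 per arm, matching the stated 50.

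**Assumptions, not in the documents.** Baseline FEV1 1.4 ± 0.45 L, Shapiro-Wilk at 5%, 1 to 6 failures set to minus baseline, and a linear model on baseline and three binary covariates.

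**1. Shape of simple ranks.** Without ties, the ranks are the integers 1 to N, whatever the data. Shapiro-Wilk on those integers gives p = 0.024 at N = 62, 0.037 at N = 56 and 0.058 at N = 50, falling below 0.05 from about N = 53. This shows that ranking yields a uniform shape. It is not the SAP's test, which is on residuals.

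**2. Ranks to litres.** With 31 per arm and normal changes, the expected difference in mean ranks is 62 × (P − 0.5), where P = Φ(0.2 / (SD × √2)) for a true 0.2 L effect.

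| SD (L) | P | Mean-rank difference |
|---|---|---|
| 0.25 | 0.714 | 13.3 |
| 0.35 | 0.657 | 9.7 |
| 0.45 | 0.623 | 7.6 |

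The same 0.2 L gives three different rank differences. With four failures added, simulation gives 11.6, 8.6 and 6.8. Conversely, three constructed data sets with identical ranks (mean-rank difference −0.548) had litre differences of 0.005, 0.016 and 0.001. A rank coefficient therefore does not determine a litre difference. The same holds for normal scores, which depend on the data only through the ranks.

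**3. How likely the fallback is.** Litre-scale residuals fail Shapiro-Wilk in about 37-98% of simulated trials, rising with the number of failures from 1 to 6. A second set of runs, with baseline 1.6 ± 0.5 L and failure probability 5-15%, gave 77-99% at N = 62 and 72-98% at N = 56. The log step may offer little rescue. A negative change has no logarithm, and with SD 0.35 L the share of negative changes is 50% if the mean change is 0 and Φ(0.2/0.35) = 72% if it is −0.2 L. If FEV1 itself were logged, the imputed zeros have no logarithm. The SAP gives no offset.

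**4. Whether ranking restores normality of residuals.** Share of trials in which ranked residuals fail, model without a treatment term:

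| N | Covariates explain nothing | Baseline explains 20% of variance |
|---|---|---|
| 62 | 42-48% | 16-20% |
| 56 | 31-36% | 11-17% |
| 50 | 21-24% | 9-13% |

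At N = 62, with covariates unrelated to change, adding treatment to the model lowers the figure to 22-26%. Over all settings for N = 50 to 62 the range is about 6-48%. Normal scores failed in 0-7% of these runs. They are no guarantee: in one extreme setting (15% failures, baseline explaining half the variance, N = 62) they failed in 44%, against 39% for simple ranks.

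**The case against.** The case for leaving the plan alone is reasonable. Rank ANCOVA is an established robust method and does not need exactly normal ranks. The SAP does not say simple ranks, and normal scores would fit its wording. It signals that the summary measure changes. The analysis is supplementary and conditional, in a study declared descriptive. The mixed model (section 14.1.3) gives an adjusted litre difference with a 95% CI. Section 14.2.2 gives the unadjusted one with its SD and CI, under the same zero imputation. All of this stands and limits the size of the point. It does not remove the conflict between sections 14 and 14.2.1, or supply the missing effect measure.

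Three stronger readings are tempting and not supported:

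- *The ranks fail the SAP's own test.* The p = 0.024 is for the integers 1 to 62. The SAP tests residuals, does not call for a re-test after ranking, and in the ranges above most trials pass.
- *The reader is left without any litre estimate.* The two analyses just named still provide one.
- *Ranking misplaces deaths.* A failure with a low baseline can rank above a survivor with a large loss; about 8-14% of failures fall outside the worst ranks on the assumed baseline. But this comes from setting FEV1 to zero while analysing change. It affects the mixed model and t-test too, and the ANCOVA adjusts for baseline.

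**Conclusion.** The point holds as a contradiction and an avoidable loss of information, of modest size. As written, sections 14 and 14.2.1 cannot both be followed, the score is unnamed, and no effect measure is defined for the ranked model. These conclusions rest on the text and need no simulation.

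That the fallback is likely (about 37-98%) and that ranked residuals may still fail (about 6-48%) rests on the assumed baseline, the number of failures, the covariate strength and a 5% test level. The SAP states none of these apart from the SD of 0.35 L. What would be lost is the litre estimate from one supplementary analysis, not the trial's only estimate of effect.

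**What to change.** In section 14.2.1, always report the untransformed ANCOVA treatment difference in litres with a 95% CI, for example a robust or bootstrap interval if normality fails. Present the rank-based ANCOVA only as an additional test and name the score, with normal scores if normality is the aim. In section 14, state that back-transformation does not apply to rank-based results.

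The cost is a few sentences of SAP text, minor programming and one extra row in a supplementary table.

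A common worst score for deaths and re-transplantations, and a Hodges-Lehmann difference, are optional. The first would need a stated litre value for failures before it could sit beside a litre-scale shift. The second is not covariate-adjusted and would add little to section 14.2.2.

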14.2.2 T-test

The mean treatment difference in change from baseline up to Week 48 in FEV_1 , standard deviation and 95% confidence interval will be presented. A two-sample t-test will be performed by treatment group at each visit using change from baseline in FEV_1 .

In case of death or re-transplantation events, FEV_1 will be imputed as zero at each nominal day post event.

14.2.3 PPS

The analysis will be conducted as described for the primary endpoint but will be performed on the PPS.

14.2.4 CCI data

The endpoint for the estimand will be spirometry data stored on the CCI. The analysis will be conducted as described for the primary endpoint but on CCI data.

14.2.5 The impact of COVID-19

The COVID-19 pandemic has impacted the conduct of the study and might have impacted its results for different aspects including infections, quarantines, social distances [4], and other considerations linked to the different ways that each site has faced the pandemic. Date of COVID-19 outbreak was set at March 11, 2020 and different analyses will be performed to assess the impact of the COVID-19 pandemic to the study pre and post pandemic. In case evidence of an impact of pandemic on study endpoints should emerge, considerations on how the initial study assumptions have been altered must be done, and changes in the statistical criteria for final judgment should be applied.

14.2.5.1 Patients impacted by COVID-19 pandemic

The analysis of primary endpoint will be performed using the LMM described in the primary analysis with the inclusion of additional categorical covariates:

- A binary covariate representing if patients have been affected by COVID-19 during the treatment period:
 - Affected, if an AE of COVID-19 is reported in the eCRF AE page between randomization and date of study completion/premature discontinuation/withdrawal of informed consent in the EOS page.;
 - Not affected, if no AEs of COVID-19 are reported in the eCRF AE page between randomization and date of study completion/premature discontinuation/withdrawal of informed consent in the EOS page..
- A binary covariate representing if patients have been randomized before or after the COVID-19 pandemic outbreak:
 - Before, if date of randomization is before 11 March 2020;
 - After, if date of randomization is equal or after 11 March 2020.

FEV₁ data will be descriptively summarized by impact of COVID-19 (COVID-19 affected vs Not COVID-19 affected, and randomized before COVID-19 Pandemic Outbreak vs randomized after COVID-19 outbreak) at each visit, by treatment and overall. The treatment comparison for difference in mean change from baseline in the FEV₁ at week 48 will be carried out using t-tests as described in section 14.2.2, including both newly created binary covariates. This will also be performed for each of the subpopulations defined by the binary covariates above i.e. patients affected/not affected by COVID-19 during the treatment period and patients randomized before/after the COVID-19 pandemic outbreak.

Furthermore, it is of interest to categorize each visit for each patient to assign these before or after the COVID-19 pandemic outbreak. A summary table will be produced to descriptively display the effects of FEV₁ over time by taking each visit with respect to the COVID-19 outbreak pandemic

L-CsA:

Treatment of BOS after SLT

Protocol Number:

BT – L-CsA – 301 – SLT

Sponsor:

Zambon SpA

date into consideration. The treatment comparison for difference in mean change from baseline in the FEV₁ at week 48 will be analyzed similarly using the t-test as described in section 14.3 for both groups, visits before COVID-19 pandemic outbreak, visits after COVID-19 pandemic outbreak.

The observed mean change from baseline and standard errors of FEV₁ at each timepoint will be graphically reported by treatment and by impact of COVID-19 categorization. This will also be displayed by COVID-19 pandemic outbreak at each visit. Furthermore, a figure with adjusted mean changes from baseline at each visit by treatment group derived from the LMM with impact of COVID-19 will be provided.

CCI

L-CsA:

Treatment of BOS after SLT

Protocol Number:

BT - L-CsA - 301 - SLT

Sponsor:

Zambon SpA

L-CsA:

Treatment of BOS after SLT

Protocol Number:

BT – L-CsA – 301 – SLT

Sponsor:

Zambon SpA

CCI

L-CsA:

Treatment of BOS after SLT

Protocol Number:

BT - L-CsA - 301 - SLT

Sponsor:

Zambon SpA

• CCI

L-CsA:

Treatment of BOS after SLT

Protocol Number:

BT - L-CsA - 301 - SLT

Sponsor:

Zambon SpA

CCI

L-CsA:

Treatment of BOS after SLT

[figure not shown]
Protocol Number:

BT – L-CsA – 301 – SLT

Sponsor:

Zambon SpA

CCl

L-CsA:

Treatment of BOS after SLT

Protocol Number:

BT - L-CsA - 301 - SLT

Sponsor:

Zambon SpA

CCI

L-CsA:

Treatment of BOS after SLT

Protocol Number:

BT – L-CsA – 301 – SLT

Sponsor:

Zambon SpA

CCI

[REDACTED]

[REDACTED]

[REDACTED]

[REDACTED]

L-CsA:

Treatment of BOS after SLT

Protocol Number:

BT – L-CsA – 301 – SLT

Sponsor:

Zambon SpA

CCI

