14.1.2 Working Hypothesis

The alternative hypothesis (H_1) for this trial is that L-CsA plus SoC is superior to SoC alone in preserving FEV₁, i.e., under H_1 it is expected that patients treated with L-CsA plus SoC will exhibit a smaller mean FEV₁ decline between baseline and the end of Week 48 than those who receive SoC alone.

Due to the decrease in sample size (see section 8.2) then there will be an underpower to assess the statistical hypothesis, and instead the primary analysis will be descriptive in nature.

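### The supplementary COVID-19 t-test cannot be run as written, and its treatment comparisons should not be adjusted for, or split by, infection status that arises after randomization

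*SAP*

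**What the plan says.** SAP 14.2.5 and 14.2.5.1 fall under Section 14.2, the supplementary analyses of the primary endpoint. They plan the following.

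- The primary linear mixed model (LMM) is re-fitted with two extra binary factors. The first is "A binary covariate representing if patients have been affected by COVID-19 during the treatment period", coded from COVID-19 adverse events recorded "between randomization and date of study completion/premature discontinuation/withdrawal of informed consent in the EOS page". The second is whether the patient was randomized before, or on or after, 11 March 2020. A figure of adjusted means from this model is planned.
- The Week 48 treatment comparison is made with the t-test of Section 14.2.2, "including both newly created binary covariates". Section 14.2.2 itself says only: "A two-sample t-test will be performed by treatment group at each visit".
- The comparison is then split: "This will also be performed for each of the subpopulations defined by the binary covariates above". That gives tests in affected and not-affected patients, and in patients randomized before and after the outbreak date.
- FEV1 is also summarized descriptively by infection status, visit and arm.
- Section 14.2.5 adds that, if the pandemic turns out to have affected the endpoints, "changes in the statistical criteria for final judgment should be applied".

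On the standing of the results, Section 14.1.2 says that "instead the primary analysis will be descriptive in nature", and the opening of Section 14 says: "As a result, all analysis for this study will be descriptive in nature".

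**The concern.** There are three separate problems.

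(a) The covariate t-test is not a defined procedure. A programmer would have to choose between an ANCOVA, another regression and a stratified test, and the SAP does not say which.

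(b) The infection factor is not a baseline characteristic. A treatment comparison that is adjusted for it, or made within its levels, no longer rests on randomization alone. A reader would take these results as showing whether COVID-19 altered the treatment effect, when they could instead reflect which patients became infected in each arm.

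(c) A sentence allowing the criteria for judgment to change, with no trigger, rule or decision-maker, does not belong in a plan that has given up a formal criterion.

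**Working it through.** **(a) The t-test.** Section 14.2.2 compares two group means of change from baseline and has no term for anything else. Section 14.2.5.1 asks for that test with two further binary factors, so the two texts cannot both be followed. In the affected and not-affected subsets the infection factor is also constant, so it could not be a covariate there under any method. Section 14.2.1 already holds a suitable model: an ANCOVA of change to Week 48 with the LMM covariates other than time, and the same zero value for FEV1 after death or re-transplantation as in 14.2.2.

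**(b) The infection factor.** Let d1 and d0 be the treatment differences among affected and not-affected patients, and p the infection rate.

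1. If each patient would be infected, and recorded as infected, equally under either arm, the affected patients in the two arms have the same expected mix of prognosis. The same holds for the not-affected. Neither subset comparison is then biased.
2. If treatment changes who is infected or recorded, those mixes can differ between arms, and d1 and d0 contain that difference. The data cannot separate this from a real difference in treatment effect by infection status.
3. If the arms are of equal size and share the same rate p, the overall difference is p × d1 + (1 − p) × d0. A simple linear model with treatment and the infection factor weights the two strata in the same proportions, so its treatment estimate equals the unadjusted one. Equal rates therefore protect the adjusted estimate in this simple case. They do not by themselves protect d1 and d0 separately, because the mix can differ at equal rates.
4. If the rates differ by arm, adjustment removes any effect of treatment that acts through infection and can also bring in the mix problem of step 2.
5. The factor for randomization before or after 11 March 2020 is fixed at randomization. Steps 2 to 4 do not apply to it.

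No size can be attached to steps 2 to 4. It would need infection rates by arm, the link between infection risk and FEV1 decline, and the effect of L-CsA on infection. The documents give none of these.

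**Precision only.** Inputs from SAP 8.2 are a difference of 200 mL, an SD of 350 mL, one-sided alpha of 0.025 and 62 patients randomized. The plan's own figure reproduces: n per arm = 2 × (1.960 + 0.842)² × (350/200)² ≈ 48.1, so 49, and 50 per arm gives power of 0.808 by the t-test. The plan states at least 80%. For 62 patients, assuming 31 per arm and no missing data:

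- SE = 350 × √(2/31) = 88.9 mL.
- The 95% half-width is t(0.975; 60) × 88.9 ≈ 178 mL for the whole trial.

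Any subset is wider. If, as an assumption, 10% to 40% of patients were affected (about 3 to 12 per arm), the affected half-width would run from about 793 to 296 mL and the not-affected from about 188 to 230 mL. These figures describe sampling error. They say nothing about bias.

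**(c) The final-judgment sentence.** Sections 14 and 14.1.2 leave the primary comparison descriptive, and Section 16 repeats this. Section 14.2.5 speaks of criteria for final judgment as though some were still in force. It does not say which criteria they are, what evidence would change them, who decides or when.

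**The case against.** The strongest reply is that the bias is hypothetical. Protocol 7.1.3 and 7.1.4 say that data so far show no increased risk of respiratory infection with L-CsA. Protocol 13.1.1.4.5 requires every confirmed COVID-19 case, in either arm, to be reported as a serious adverse event, which limits differential recording. Under SAP 8.4 the data monitoring committee compares case rates by arm. This largely stands, with two limits. Protocol 9.2 itself raises infection as a possible risk of a sucrose-containing formulation given without the drug, so an effect on infection is not excluded. And a comparison of rates does not show which patients were infected.

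A second reply is that the plan wants to learn about infection, and the before/after factor cannot do that. It also counts as before the outbreak those patients randomized earlier whose later visits fell within it. This is correct and is a real cost of the change.

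Three stronger readings are tempting, and the documents do not support them.

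- A reader might infer that the adjusted LMM is shown to be biased. It is not. With equal arm sizes and infection rates the simple adjusted estimate equals the unadjusted one, and nothing in the documents shows unequal rates.
- A reader might infer that the infection factor counts infections after the Week 48 FEV1, because its window ends at the end-of-study date. The text does not settle this. Protocol 10.3.4 treats patients as completers at Visit 9, patients entering BOSTON-3 have no later visit, and SAP 15.2.2 treats standard of care as running through the whole study period. Ending the factor at Week 48 would be undefined for patients without a Week 48 value and would leave the by-visit tables with the same feature at earlier visits.
- A reader might infer that the final-judgment sentence lets the sponsor move a success threshold. With the analysis declared descriptive there is no threshold to move, and SAP 5 requires SAP changes to be documented with timing and rationale. What remains is a conflict of wording.

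**Conclusion.** The point holds as a matter for consideration, limited to supplementary analyses. The primary LMM of Sections 14.1.3 and 14.1.4 has no COVID-19 term and is not affected.

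The covariate t-test is wrong as written, and this follows from the text with no assumption. The adjusted estimate and the two infection-status tests lack the protection of randomization. Whether they are biased depends on an effect of treatment on infection or its recording that the documents do not show, and the size of any bias cannot be derived. The final-judgment sentence is inconsistent with the descriptive status of the plan and has little to act on.

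**What to change.** - Replace the covariate t-test in SAP 14.2.5.1 with the Section 14.2.1 ANCOVA plus the factor randomized before versus on or after 11 March 2020.
- In the supplementary LMM, and in the adjusted-mean figure drawn from it, keep only that factor.
- Run no treatment test within affected or not-affected patients. Tests by randomization before or after the outbreak date may stay.
- Keep the planned descriptive FEV1 summaries by infection status and arm, and add COVID-19 incidence by arm.
- Delete the sentence in Section 14.2.5 on changing the criteria for final judgment.

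The cost is SAP wording only, with no new data. One supplementary adjusted estimate and two subset tests are lost, and infection itself is then examined only descriptively.
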